OPRI
Study protocol

Study protocol

*ICARUS: Inhaled
Corticosteroid And Real life
Unlicensed Spacer use –
stage 2*

*Studying the adverse events in real-life unlicensed
and licensed use of inhaled corticosteroids with
spacers in patients with asthma in the United Kingdom*

Date:
28th October 2016

Chiesi contact:
[name]

Chief Investigator:

[name], Professor of Primary Care Respiratory Medicine and OPRI Director

[contact]

Office number: [name]

Skype ID: [name]

Email: [contact]

Project coordinator:

[name]

Observational and Pragmatic Research Institute

[name]

Direct number: [name]

Email: [contact]

Study sponsor:

Chiesi Ltd

Primary contact

[name]

TITLE	ICARUS: Stage 2
Subtitle	Examining the real-life unlicensed and licensed use of inhaled corticosteroids with spacers in patients with asthma in the United Kingdom
Protocol version number	1.3
Medicinal product	Clenil (beclomethasone dipropionate)
Medical device	Aerochamber, Volumatic spacers
Marketing authorisation holder	Clenil: Chiesi Limited [name]
Study aims and objectives	The aim of this study is to compare matched patients that are treated with non-extrafine beclomethasone dipropionate with a Volumatic® spacer against patients that are treated with non-extrafine beclomethasone dipropionate with an Aerochamber® spacer. As a subquestion, patients prescribed Aerochamber® and Volumatic® who step down their inhaled corticosteroids will be compared in terms of baseline asthma exacerbations and SABA usage
Country of study	UK
Author	OPRI [name]

3.0 Background

Asthma is considered a heterogeneous obstructive lung disease caused by an inappropriate inflammatory reaction in the airways. Increased mucus production and bronchospasm can lead to exacerbations and significant mortality. Narrowed airways can result in reduced quality of everyday living – the Royal College of Physicians three questions surveys whether asthma is controlled by asking the patient whether they have nocturnal disturbances, whether asthma limits activity, and whether they suffer from any daytime symptoms. Treatment of asthma is centered around the use of inhaled corticosteroids, which are recommended in all but the mildest patients with asthma¹. The latest GINA guidelines recommend patients who require their reliever more than once a fortnight be prescribed inhaled corticosteroids¹. Reducing the inflammatory response not only helps control the disease, prevents exacerbations and reduces the daily symptoms, but also might help to reduce any chronic changes that occur as a result of long term inflammation.

However, the use of corticosteroids can cause significant side effects, especially when prescribed to young children or when higher doses are required. Inhaled corticosteroids are dispensed at significantly lower doses than oral corticosteroids, significantly reducing the risk of glucocorticoid side effects compared to oral therapy ²(Table 1).

System Class	Adverse Reaction	Frequency
Infections	Oral thrush	Very common
Immune system	Rash, urticarial, pruritus, erythema	Uncommon
	Oedema	Very Rare
Endocrine	Adrenal suppression, bone density reduction, growth retardation	Very Rare
Psychiatric disorders	Psychomotor hyperactivity, sleep disorder, depression, anxiety, behavioural disorders	Unknown
Nervous system disorders	Headache	Unknown
Eye disorders	Cataracts, glaucoma	Very Rare
Thoracic disorders	Hoarseness, throat irritation	Common
	Cough, bronchospasm, wheezing, dyspnoea	Very rare
Gastrointestinal	Nausea	Unknown

Table 1: Side effects of non-extrafine beclomethasone dipropionate listed by system ³

Unlike oral therapy, the use of inhaled corticosteroids requires a meaningful delivery of the drug to the lungs, which requires good adherence and a proper inhaler technique from the

patient. Up to 80% of the inhaled drug ends up impacting in the oropharynx and being systemically absorbed, even when good technique is used. Accordingly, spacer devices are suggested to improve drug delivery to the lungs⁴.

Spacer devices are an extension add-on device that allows the aerosol from metered dose inhalers to expand and slow down. This effect changes the actuation spray into a fine mist, allowing more time for the evaporation of the propellant, so a larger proportion of the particles can be inhaled. A fine mist is less likely to impact the oropharynx and reach the target of the lungs. Spacers also help to coordinate the breathing between actuation and breath. The use of bronchodilators and spacers is on par to that of nebulisers in terms of effectiveness⁵. The improved drug delivery from using a spacer in conjunction with a pMDI can help reduce the amount of inhaled corticosteroid required.

The use of spacers is recommended by NICE for patients aged under 16 with the following guidance⁴:

Inhaler devices for children under 5 years with chronic asthma (August 2000)

A child's needs and likelihood of good compliance should govern the choice of inhaler and spacer device; only then should cost be considered.

- corticosteroid and bronchodilator therapy should be delivered by pressurised metered-dose inhaler and spacer device, with a facemask if necessary;

Inhaler devices for children 5–15 years with chronic asthma (March 2002)

A child's needs, ability to develop and maintain effective technique, and likelihood of good compliance should govern the choice of inhaler device; only then should cost be considered.

- corticosteroid therapy should be routinely delivered by a pressurised metered-dose inhaler and spacer device;
- for other inhaled drugs, particularly bronchodilators, a wider range of devices should be considered;
- children and their carers should be trained in the use of the chosen device; suitability of the device should be reviewed at least annually. Inhaler technique and compliance should be monitored.

Figure 1: NICE guidance for spacer use in children

Spacers are also advised for patients who have problems with co-ordinating actuation since they are simpler to use. They are also advised to be used in adult patients using high doses of inhaled corticosteroids (cut off defined as 500 µg fluticasone/1000 µg beclomethasone

dipropionate equivalent or higher)⁶. Finally, elderly patients, those with false teeth or mouth/lip structural damage, or those unable to coordinate activation with respiration are suitable candidates for an spacer.

There are several brands of spacers that fit different inhalers as shown in Table 2:

MDI	Able spacer	Aerochamber Plus	Optichamber	Pocket Chamber	Volumatic
Beclomethasone Dipropionate (Clenil Modulite)	a	a	a	a	✓
Beclomethasone Dipropionate HFA	a	✓	a	a	✗
Fluticasone propionate	a	✓	a	a	✓
Ciclesonide	a	✓	a	a	✗
Beclomethasone/ formoterol	a	✓	a	a	✗
Fluticasone propionate / formoterol	a	✓	a	a	✗
Fluticasone propionate / salmeterol	a	✓	a	a	✓

Table 2: Spacer and suitable MDI devices

a = fits spacer but not licensed for use ✓ = licensed for use ✗ = does not fit spacer

The license for non-extrafine beclomethasone dipropionate (Clenil Modulite) with the Volumatic spacer, but it has also been shown to be prescribed off-license for Aerochamber, in previous unpublished research from OPRI (formerly Research in Real Life). There is a concern that the use of some spacers may result in a greater number of adverse events; larger spacers such as the Volumatic[®] spacer have been shown to feature a lower deposition of drug on the filters compared to the use of smaller spacers and thus less more effective distribution².

In real-life practice, the effectiveness of any device combination depends on the willingness and ability of the patient to use it⁷. Patients may not use the spacers correctly in a number of ways as described in Table 3:

Errors with spacer devices
Placement of inhaler in the wrong end of the spacer
Failure to exhale slowly
Failure to shake inhaler well
Waiting too long before inhaling
Pressing too many times on the MDI
Rapid inhalation

Exhaling into device
Inadequate breath hold

Table 3: Spacer errors ⁷

In addition, primary care physicians who prescribe spacers may not adhere to prescription guidelines given that their patients may be unwilling to carry or use the devices.

In stage 1 of this study, a significant number of patients prescribed spacers and non-extra-fine beclomethasone dipropionate off license were found. Stage 2 will focus on comparing the adverse events between non-extra-fine beclomethasone dipropionate prescribed using the Volumatic[®] spacer and the Aerochamber[®] spacer.

For this study, database outcomes and patient questionnaires will be examined. Asthma questionnaires have been used in quality of life reviews⁸, randomised controlled trials⁹ and have been an essential component for improving asthma care in the United Kingdom ¹⁰.

Patient-reported side effects will provide a unique perspective to disease outcomes compared to database Read codes, where bruising for example is seldom reported. An extract of the adult and child questionnaire is shown below (Figure 2 and Figure 3).

Do you experience any of these side effects from your preventer inhaler? Please tick yes or no for each one

	Yes	No		Yes	No
Continual sore mouth/throat			Hoarse voice		
Oral Thrush			Abnormal Weight Gain		
Bruising			Cough		

Figure 2: British Lung Foundation asthma questionnaire extract for adults

Does your child experience any of the following side effects from their preventer inhaler? Please tick Yes or No for each one

	Yes	No		Yes	No
Continual sore mouth or throat			Hoarse voice		
Oral thrush			Abnormal weight gain		
Bruising			Cough		

Figure 3: British Lung Foundation asthma questionnaire extract for children

4.0 Study aims and objectives

4.1 Study aims

The aim of this study is to characterise the adverse events in patients with asthma treated with non-extra fine beclomethasone dipropionate with Volumatic[®] spacer or Aerochamber[®] spacer.

In addition, as an additional question, the study will also attempt to explore whether

Aerochamber patients experience increased efficacy leading to their daily dose of non-EF beclomethasone being changed (stepped down or titrated down) compared to Volumatic users.

4.2 Study objectives

4.2.1 Primary objective

Non-inferiority of non-extrafine beclomethasone dipropionate with Aerochamber[®] spacer compared to non-extrafine beclomethasone dipropionate with Volumatic[®] spacer, in terms of the rate of patient-reported outcomes listed on the British Lung Foundation Questionnaire, ie the incidence of oral thrush or hoarseness.

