5.2 Study design (questionnaire outcomes)

A longitudinal study to compare patient-reported side effects for asthma patients prescribed non extra fine beclomethasone with Volumatic[®] spacer or Aerochamber[®] spacer (Figure 4). The index date of the study is the date of administration of the BLF Questionnaire. This study design will also be used to explore patients who step down at the index date with Volumatic and Aerochamber spacers. This exploratory objective will explore the baseline year (ie: year before index) in terms of comparative efficacy. If required (due to insufficient patients) an additional study design will be incorporated which will consider date of step down as index date (instead of date of BLF questionnaire).

[figure not shown]

Figure 4: Study Design (questionnaire outcomes)

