8.4 Analysis of study outcomes

8.4.1 Primary analysis: Questionnaire based adverse events

Adverse events as total and individual events in the questionnaires will be compared using a conditional Poisson regression model. The model will use empirical standard errors and adjustments will be made for potential baseline confounders.

The adjusted rate ratio with 95% confidence interval will be reported.

Non-inferiority in patient reported adverse events (oral thrush OR hoarseness) will be achieved if the proportion of Clenil/Aerochamber is no more than 13% higher (based on the upper boundary of the 95% confidence interval) than the proportion of patients on Clenil/Volumatic.¹⁴

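### The primary objective claims non-inferior incidence, but the single yes/no questionnaire item supports only a comparison of the proportion reporting thrush or hoarseness, and the only confidence interval the plan promises is for a ratio, while the margin is a difference

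*Protocol*

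**What the plan says.** Protocol Section 4.2.1 seeks non-inferiority of Aerochamber to Volumatic in the rate of outcomes that patients report on the questionnaire, "ie the incidence of oral thrush or hoarseness".

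The instrument is extracted in Section 3.0 (Figures 2 and 3). Adults are asked "Do you experience any of these side effects from your preventer inhaler? Please tick yes or no for each one"; the parent version reads "Does your child experience any of the following side effects from their preventer inhaler? Please tick Yes or No for each one". Both are in the present tense, and neither extract asks when the symptom began, over what period it is recalled or how many episodes there were.

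Section 5.2 fixes the timing: "The index date of the study is the date of administration of the BLF Questionnaire". Section 6.1 requires two years of records before the questionnaire and a spacer prescribed at some earlier time. It requires nothing after the questionnaire. By contrast, the database study in Section 5.4 has a three-year outcome period after index.

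For the analysis, Section 8.4.1 specifies conditional Poisson regression with empirical standard errors and states: "The adjusted rate ratio with 95% confidence interval will be reported". It then declares non-inferiority if the Aerochamber proportion with thrush or hoarseness is no more than 13% higher than the Volumatic proportion, judged on the upper 95% bound. Section 8.1 powers a test of two proportions with a margin of 0.130 on the difference.

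**The concern.** Three terms are used for one primary endpoint: an incidence in the objective, a rate ratio in the reported result, and a proportion in the decision rule. Only the last can be obtained from the questionnaire as described.

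An incidence needs new cases counted over a known time at risk. The text gives no start of risk time, no exclusion of patients who already had the symptom and no second questionnaire, so new and existing complaints cannot be separated. The proportion answering yes depends on how often the symptom starts and on how long it lasts.

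This is a safety claim about a combination that Section 3.0 describes as off-licence. A report written to Section 4.2.1 would say that Aerochamber does not unacceptably raise the incidence of local side effects, which the data do not show without a further assumption about duration. In addition, the only interval that Section 8.4.1 promises is on the ratio scale, so the reader would not see the quantity the margin refers to.

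**Working it through.** **1. The plan's own figure.** Inputs from Section 8.1: groups of 293 and 147, proportion 0.30 in both groups (expected difference 0), margin 0.130, one-sided level 0.025.

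- Standard error = √[0.30 × 0.70 × (1/293 + 1/147)] = √0.002145 = 0.0463
- Power = Φ(0.13/0.0463 − 1.96) = Φ(0.847) = 0.801

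The stated 80% is reproduced. The calculation is entirely in proportions of patients, with no person-time, so naming the endpoint a proportion leaves 293/147 and the power as they are.

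**2. What an incidence would need.**

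| Needed | What the protocol text gives for the questionnaire comparison |
|---|---|
| Onset date or recall window | None in the extracted items (3.0) |
| Start of time at risk | Spacer prescribed at any earlier time (6.1) |
| Symptom-free at start | No such criterion (6.1) |
| Follow-up or repeat measurement | Index date is the questionnaire date (5.2); required data lie before it (6.1) |

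No incidence can be computed from these inputs.

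**3. The margin on the two scales.** An absolute margin of 0.13 corresponds to different ratios at different Volumatic proportions. Both proportions below stand in Section 8.1.

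- At 0.30: (0.30 + 0.13)/0.30 = 1.43
- At 0.34: (0.34 + 0.13)/0.34 = 1.38

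If someone holding only a ratio interval read the 13% as relative, the limit would be 1.13, or 0.30 × 1.13 − 0.30 = 0.039 at a proportion of 0.30. That is 3.9 points rather than 13. Section 8.1 makes clear that the absolute reading is the one the study is sized for, but Section 8.4.1 does not say so and promises no interval for a difference.

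**4. How far prevalence and incidence can part (illustration only).** This rests on an assumption that is not in the documents: a steady state in which prevalence odds = incidence × mean duration. The duration ratios (Aerochamber over Volumatic) are also assumed; the protocol gives none. Volumatic prevalence is set at 0.30, so its odds are 0.30/0.70 = 0.4286. With equal incidence, Aerochamber odds = 0.4286 × duration ratio and prevalence = odds/(1 + odds). With equal prevalence, incidence ratio = 1/duration ratio.

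| Duration ratio | Aerochamber prevalence at equal incidence | Difference, points | Incidence ratio at equal prevalence |
|---|---|---|---|
| 0.5 | 17.6% | −12.4 | 2.0 |
| 0.8 | 25.5% | −4.5 | 1.25 |
| 1.0 | 30.0% | 0 | 1.0 |
| 1.25 | 34.9% | +4.9 | 0.8 |
| 2.0 | 46.2% | +16.2 | 0.5 |

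The two measures agree when durations are alike and diverge in step with the duration ratio.

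**The case against.** The strongest reply is that every operative passage already works in proportions. The power calculation is a test of proportions, the decision rule names the proportion, and the composite of thrush or hoarseness is the same in Sections 4.2.1 and 8.4.1. A reader might infer from the mismatch that the primary analysis can support no conclusion. The documents do not bear that out: one yes/no answer per patient is enough for a non-inferiority conclusion on the proportion reporting the symptom. This part of the objection stands and limits the point to the scope of the claim and the scale of the reported interval.

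Four further points are fair.

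- It is tempting to call the measure a point prevalence. The item does not say today or now and can be read as habitual experience, and Section 3.0 shows only an extract, so instructions elsewhere on the form cannot be excluded. The safe description is the proportion reporting the side effect at the questionnaire.
- Section 5.2 opens with "A longitudinal study to compare patient-reported side effects for asthma patients". A reader might call that label wrong, but linked records from the preceding years are used for baseline variables and the step-down question, so the word is defensible.
- Poisson regression with empirical standard errors is an accepted way to model a binary outcome. Without a time offset, the exponentiated coefficient is a ratio of proportions. The model is not at fault; the name of its output is.
- Nothing in the protocol suggests that symptom duration differs by spacer. A reader might also argue that a 1.5-fold incidence with equal duration gives 39.1%, only 9.1 points higher, and so slips under the margin. It does not, because the rule uses the upper bound. With 39.1% against 30% and the planned sizes, the standard error is 0.047 to 0.048 depending on which group is larger, and the chance of declaring non-inferiority is Φ((0.13 − 0.091)/SE − 1.96), about 12 to 13%.

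The objection does not remove the wording of Section 4.2.1. The objective is fixed in the protocol, and no later analysis plan can recover onset or time at risk that the questionnaire does not record.

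**Conclusion.** The point holds as a mismatch between the claim and the measurement. As written, Section 4.2.1 promises a conclusion on incidence, while the questionnaire supports one on the proportion of patients reporting thrush or hoarse voice. Section 8.4.1 promises an interval for a ratio, while the margin is an absolute difference of 0.130, equivalent to a ratio of 1.43 at 0.30 and 1.38 at 0.34.

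The numerical plan is unaffected: 80.1% power against 80% stated, taking the plan's own two-group calculation. No bias of known size can be attached to the incidence wording, because the documents give no durations; the illustration shows direction and range only.

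The conclusion assumes a single measurement occasion. That rests on the text of Sections 5.2 and 6.1, since the design diagram (Figure 4) is not available, and on the extracted items being complete as to recall period. The change should be made before the report is written, because it governs the headline safety statement.

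**What to change.** - **Section 4.2.1:** replace the rate and incidence wording with the proportion of patients reporting oral thrush or hoarse voice at the questionnaire (prevalence), and limit the non-inferiority claim to that proportion.
- **Section 8.4.1, reported measure:** for the binary primary endpoint, call the exponentiated model coefficient a ratio of proportions.
- **Section 8.4.1, decision rule:** state that the difference in proportions, Aerochamber minus Volumatic, is reported with its 95% confidence interval, and that its upper bound is compared with 0.13 as an absolute difference. How the adjusted difference is estimated in the matched data can be left to the analysis plan.
- **Incidence language:** reserve it for the three-year database outcomes, which have follow-up after index.

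No new data and no change in sample size are needed. The cost is a few sentences and a narrower primary claim.

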4.2.2 Secondary objective

Comparison of database outcomes for non-extrafine beclomethasone dipropionate with Volumatic[®] spacer and non-extrafine beclomethasone dipropionate with Aerochamber[®] spacer in terms of Read codes for adverse reactions to beclomethasone dipropionate over a three-year period.

4.2.3 Exploratory objective

Patients who step down their prescribed dose of non-extra fine beclomethasone dipropionate with Volumatic[®] and Aerochamber[®] will be compared in terms of baseline exacerbation rate and SABA usage.

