7.3 Questionnaire outcomes

Total and individual questionnaire related outcomes for

- 1) Continual sore mouth or throat
- 2) Oral thrush
- 3) Hoarse voice

* Calculated as average number of puffs per day over the year multiplied by strength (in µg);

[†] See appendix 1 for definitions

i.e. $\frac{\text{Number of inhalers} \times \text{doses per inhaler}}{365} * \text{strength}$

- 4) Bruising
- 5) Abnormal weight gain
- 6) Cough

As an exploratory outcome, the prescribed ICS dose at index dose will be considered to create the subgroups of step down patients for the Volumatic and Aerochamber spacers.

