7.5 Step down outcomes

- 1) Number of severe exacerbations in baseline year
- 2) Daily average SABA category in baseline year

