8.4.2 Secondary analysis – database outcomes

The total number of adverse events as listed in the Summary of Product characteristics in the outcome period will be compared between treatment groups compared using a conditional

Poisson regression model. The model will use empirical standard errors and adjustments will be made for potential baseline confounders.

The adjusted rate ratio with 95% confidence interval will be reported.

Exploratory analysis – The exacerbation rate and separately the daily SABA dosage for patients during the baseline year who step down ICS at the index date treated with an Aerochamber spacer will be compared to patients prescribed a Volumatic spacer and compared with a Wilcoxon ranked test.

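### The exploratory step-down analysis selects on step-down and compares the year before it, so it cannot answer the section 4.1 question of whether Aerochamber users step down more

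*Protocol*

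**What the plan says.** Section 4.1 of the protocol adds a question to the main aim: whether "Aerochamber patients experience increased efficacy leading to their daily dose of non-EF beclomethasone being changed (stepped down or titrated down) compared to Volumatic users". Step-down is the consequence of interest there, and it is to be contrasted between spacers.

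The sections that put this into practice use step-down differently:

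- Section 4.2.3 sets the population as "Patients who step down their prescribed dose of non-extra fine beclomethasone dipropionate", in each spacer group, and says that they "will be compared in terms of baseline exacerbation rate and SABA usage".
- Section 5.2 places step-down at the index date, which is the questionnaire date, and adds: "This exploratory objective will explore the baseline year (ie: year before index) in terms of comparative efficacy". If numbers are too small, a further design would take the date of step-down as the index date.
- Section 7.3 says that the steroid dose prescribed at index "will be considered to create the subgroups of step down patients for the Volumatic and Aerochamber spacers".
- Section 7.5 is titled as step-down outcomes, but its two items are "Number of severe exacerbations in baseline year" and the SABA category in the same year.
- Section 8.4.2 names a Wilcoxon test in which patients "who step down ICS at the index date treated with an Aerochamber spacer will be compared to patients prescribed a Volumatic spacer".

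The last mock table in section 15.2 has step-down and non-step-down columns for each spacer, a total row with percentages, and a single p-value column across the four groups.

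**The concern.** The variable that section 4.1 asks about is used only to choose the patients, and the variables tested precede it. A null result among step-down patients could sit beside a large gap between spacers in how often patients step down. A positive result could arise with identical step-down frequencies, for instance if prescribers reduce the dose at different levels of control in the two groups. Either result could be reported under the comparative-efficacy label of section 5.2 and taken as an answer to section 4.1, which it is not.

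**Working it through.** **1. The plan's own figure.** The protocol gives no power or sample size for the step-down question. Its only power figure (section 8.1) is for the primary comparison: groups of 293 and 147, proportion 0.300, true difference 0, margin 0.130, one-sided 0.025. The standard error is sqrt(0.3 × 0.7 × (1/293 + 1/147)) = 0.0463. Power is Phi(0.130/0.0463 − 1.96) = 0.801, so the stated 80% reproduces. It has no bearing on this point except that the group sizes are borrowed in step 4.

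**2. The two quantities side by side.** Write X for spacer, S for step-down (yes/no) and B for baseline-year exacerbations or SABA use.

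- Section 4.1 concerns P(S=1 | X = Aerochamber) against P(S=1 | X = Volumatic).
- Sections 4.2.3, 7.5 and 8.4.2 compare the distribution of B given S=1 between the two values of X.

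The sentence in section 8.4.2 does not repeat the step-down restriction for the Volumatic arm, but sections 4.2.3 and 7.3 apply it to both. On either reading, no frequency of step-down is compared.

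**3. Why one does not inform the other.** By Bayes' rule,

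P(B | S=1, X) = P(S=1 | B, X) × P(B | X) / P(S=1 | X).

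Multiply P(S=1 | B, X) by a constant c in one spacer group, keeping probabilities at or below 1. P(S=1 | X) is multiplied by c as well, and c cancels. Step-down frequency in that group can therefore double or halve while the distribution being tested stays the same. Conversely, the tested distribution can differ because P(B | X) differs or because P(S=1 | B, X) depends differently on B, with no difference in P(S=1 | X). This needs no numerical assumption.

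**4. Illustration.** The inputs are assumed and are not in the protocol: 293 Aerochamber and 147 Volumatic users (sizes from section 8.1, allocation to spacer assumed), the step-down shares shown, and Poisson baseline exacerbations among step-down patients with the means shown. There were 2,000 runs per row, with two-sided tests at 5%. The first test is the planned Wilcoxon test on exacerbations among step-down patients; the second compares step-down proportions over all users.

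| Step-down share, Aerochamber v Volumatic | Baseline mean among step-downs | Planned Wilcoxon rejects | Proportion test rejects |
|---|---|---|---|
| 20% v 20% | 0.3 v 0.3 | 4.7% | 5.7% |
| 30% v 15% | 0.3 v 0.3 | 4.9% | 95.1% |
| 40% v 20% | 0.3 v 0.3 | 4.3% | 99.3% |
| 20% v 40% | 0.3 v 0.3 | 4.6% | 99.1% |
| 20% v 20% | 0.3 v 0.8 | 83.2% | 5.8% |

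The planned test stays at its null level when the share doubles or halves, and rejects often when the shares are equal but baseline values differ.

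**5. Why the efficacy reading also fails.** Section 6.1 requires the spacer at some time before the questionnaire, with no minimum interval, so the baseline year need not be a year on the spacer. Section 8.3 makes matching for this question conditional on numbers, and section 8.4.2 names no adjustment for it.

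**6. Where a denominator exists.** Section 6.1 (questionnaire cohort) does not require step-down, so non-step-down users are present. Section 6.2 (database cohort) lists step-down during follow-up as an inclusion criterion; as written, everyone there has stepped down and no proportion can be formed.

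**The case against.** The synopsis and sections 4.2.3, 7.5 and 8.4.2 agree with one another: they describe a comparison of baseline exacerbations and SABA use between step-down patients on each spacer. Only the additional question in section 4.1, which the study says it will attempt to explore, reaches further. The work is exploratory, and rewording that one sentence would remove the mismatch. All of this stands. It locates the fault in the conflict with section 4.1 and limits its weight, but does not make the planned test answer the question posed there.

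Four stronger readings are tempting, and the documents do not support them.

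- A reader might infer that selecting step-down patients forces both groups to look well controlled whatever the spacer does. The protocol gives no criterion for step-down, and the last row of the table shows that the test can detect a baseline difference among such patients. It answers another question; it is not blind.
- A reader might build an example with annual exacerbation means of 0.3 and 0.5 and step-down only after an exacerbation-free year: exp(−0.3) = 0.741 and exp(−0.5) = 0.607, a 13-point gap in eligibility, with zeros compared with zeros. That result restates the assumption, and it ignores SABA use, the second outcome.
- A reader might say that step-down frequency would never be visible. The last mock table would show the counts for each spacer. What is missing is a defined outcome, an effect measure and an interval.
- A reader might say that the questionnaire date is the only anchor for step-down. Section 5.2 offers the step-down date as an alternative, conditional on insufficient numbers. That alternative still analyses only patients who stepped down.

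**Conclusion.** The point holds as a mismatch between a stated question and the analysis meant to explore it. The planned comparison carries no information on whether step-down is more frequent with one spacer. That conclusion follows from the conditioning alone; the simulated rejection rates (4–5% for the planned test against 95–99% for proportions when shares differ twofold) illustrate it under assumed inputs and are not predictions for this study. Nor should the comparison be presented as comparative efficacy. It is worth correcting because the protocol itself fixes the population, outcomes, timing and test. The primary non-inferiority conclusion and the secondary analysis are not affected.

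**What to change.** In the questionnaire cohort of section 6.1, define step-down (yes/no, in a fixed window) as the exploratory outcome among all eligible or matched users of each spacer. Report the proportion by spacer with a risk ratio and 95% CI, adjusted for the available baseline covariates.

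Two details need settling. Section 6.1 guarantees only two years of data before the questionnaire, so a window running past that date would need an added data requirement. Adjustment for pre-spacer exacerbations and SABA use is possible only where the spacer date and the data history allow; values measured after the spacer was prescribed may already reflect it.

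Keep exacerbations and SABA use among step-down patients as description, and drop the comparative-efficacy wording in section 5.2. Do not use the database cohort for this question unless the step-down inclusion criterion in section 6.2 is lifted for this analysis.

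If none of this is done, reword section 4.1 as a description of patients who step down. The full change costs one exploratory model and its outcome definition; the rewording costs one sentence.
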